3.2 Inclusion and excluding criteria

Participant inclusion criteria; the participants have to be on sick leave or be in danger to be on sick leave because and obesity related problems. The participants have to have a real opportunity for returning to work, full time or part time. The participants have to have a BMI above 30 and be in age between 18 to 67 years old.

Participants excluding criteria;

1. People with a severe eating disorder.
2. People who cannot consent.
3. People with a severe alcohol and drug abuse.
4. People with a severe psychiatric disease.
5. Pregnancy
6. People with a health condition that contraindicates physical activity.
7. People who receive work assessment allowance.
8. People with or wants so seek for disability benefits.
9. People with permanently organized work.

3.3 Recruiting of participants

Recruiting participants in this study are as followed:

1. Before the first stay at Muritunet. The patients will receive an envelope with written information by post a month before their stay. In the envelope, there are two letters. One with detailed information about the study and one letter with a request to consent to the research. After the participants arrive Muritunet, they will receive information about the study, attachment one, given by project secretary. Those who want to participate in the study gives written consent. The project secretary registers the written consents in SPSS at Muritunet. SPSS is a comprehensive software package for statistical analysis and data management.
2. For participants who participate or are finished with the stay at Muritunet. The participants receive by post a written letter with detailed information about the study and two letters with a request to consent in the study. In addition to the letters, there is a prepaid envelope with the address to Muritunet, attachment one. If the person approves to participate in the study, he or she signs the consent and returning it to Muritunet. The project secretary registers the agreement in SPSS. This registration goes to the researcher who can call the participant regarding interview.

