Will change in lifestyle have a correlation with ability to work? Life style factors that affect work participation

Occupational rehabilitation for people with body mass index
above 30

Summary

This trial will follow up a group of people with BMI above 30 and who have participated in an occupational rehabilitation program at Muritunet. The aim of this study is to gather information about how life style changes affect the ability to work.

Ver.2.0, 24.7.2017

[name]
[contact]

1 Introduction

Numbers from Statisk Norway indicate that one out of three has overweight (BMI >25) or obesity (BMI >30) in the population in the age of 16 to 74 [1]. Development of overweight and obesity have the latest years dramatically increased. In Norway, the consequences of this development is an epidemic situation with an increase in life style diseases and work absence. Central Norway Regional Health Authority (HMN RHF) has initiated action to reduce work absence and consequence of obesity by introducing a work related rehabilitation program for people with BMI above 30. Combination of weight loss programs and work related intervention is new in Norway. Outcomes of this intervention are so far are not known.

The trial can be used to improve the quality of occupational rehabilitation in Norway in the Specialised Health Care services. Others who work with life style changes and with work related rehabilitation can also use the collected information. This study is a Cohort clinical trial with a Pseudo prospective design.

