3.1 Design, methods and analyze

This study will follow-up a group of people with BMI above 30 over a period of one to four years. Study with a Pseudo prospective design that includes collecting data through both qualitative and quantitative methods. Both methods will take place at the same time, Parallel mixed Methods. The data is linked to each other in the different stages in the study, and the methods will confirm, cross-validate or confirm findings in one method with another result in another process. Creswell uses the Current concept Triangulation [30]. The purpose of this plan is to make one method stronger with using the strength of another method.

The definition of Mixed Method research in this study is; Approach to gathering data through quantitative and qualitative methods with the use of designs that involve both philosophical and ethical theory [31].

Collecting data through forms, physical test, journal, interviewing, from national register from the Norwegian Labour and Welfare Administration and National

Education Data Base. Using registry data will be useful because there might be a link between different variables that might contribute to clarify the association between health and work participation. It then can be specified whether the participant is on sick leave because of obesity related issues or if there are other reasons for the sick leave. Another example is the connection between education and work participation because the level of education may have importance for choice of profession and sick leave. There are several links in this study that can strengthen the findings in the data collection.

Data collected at four different stages.

1. Baseline (BL). From the beginning of the stay at Muritunet. Data gathered from the journal, from self-reported forms, and from a physical test. The particular data package is; in and out date for the stay, age, sex, diagnosis, education level, health problems, work status, social benefits, changing in work status, work place, expected work time pr. Week and occupation code, work motivation, income, diet, physical capacity and activity, life quality and overeating behaviour.

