3.10 Calculation of sample size

The calculation of the sample size on a group basing on previously participated in a similar occupational rehabilitation intervention for people with a BMI above 30 at Muritunet. The research question is leading for the sample size. The calculation is based on the time for data collection baseline and at the end of the intervention at Muritunet T3. The calculation is basing on apriority effect size, p value =0,05 and 80 percent statistical strength.

Goal of changing

1. Work; With a statistical power of 80,4 percent to achieve a clinical and a statistically significant change in 25 percent increasing work participation this study has to have 51 participants with two end point. The calculation is made out of 95 percent confidence interval (95% CL=18,05-31,95).
2. Weight reduction; With a statistical power of 80,2 percent to achieve a clinical and a statistically significant change in 11 kg weight reduction this study has to have 59 participants with two end point. The calculation is made out of 95 percent confidence interval (95% CL=6,82-15,18).
3. Quality of life; With a statistical power of 80,7 percent to achieve a clinical and a statistically significant change on 0,02 this study has to have 55 participants with two end point. The calculation is made out of 95 percent confidence interval (95% CL=0,025- 0,045). In the foam Quality of Life 15D, the SMR is the smallest clinical relevant change 0,015.

This calculation is done with the use of SPSS Sample Power program.

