3.11 Organization and cooperation

Volda University College is responsible for this study. [name] is the project manager and the Ph.D. student. This study is a partnership between Volda UC and Muritunet. The participants are collected from an occupational rehabilitation program for people with a BMI above 30. Data from

baseline, T1, and T2 is from the participants stay at Muritunet. T3 happens where the participants live. T4 is from two different registers. The Ph.D. student is a full-time employee with Volda UC, but work 25 percent at Muritunet.

This study links to Regional Centre for Obesity Research and Innovation at St.Olavs Hospital in Trondheim, and the National Competence Centre for Work-Based Rehabilitation in Rauland.

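### Some participants consent by post during or after the stay, when they may know their outcome, and the protocol does not separate them from those recruited beforehand

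*Protocol*

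**What the plan says.** Protocol section 3.3 sets out two recruitment routes.

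- **Route 1, before the stay.** "The patients will receive an envelope with written information by post a month before their stay". Written consent follows after arrival, once the study has been explained. No outcome exists at that point.
- **Route 2, during or after the stay.** "For participants who participate or are finished with the stay at Muritunet". The invitation is posted to them, and the enclosed letters ask for consent to the study as a whole. Joining is an act of the participant: "If the person approves to participate in the study, he or she signs the consent and returning it to Muritunet".

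The introduction states the design openly: "This study is a Cohort clinical trial with a Pseudo prospective design". Section 3.11 says that the data from "baseline, T1, and T2 is from the participants stay at Muritunet". For someone who has finished, these data therefore exist before consent is asked for.

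Nothing after section 3.3 distinguishes the routes. Section 3.1 speaks of one group: "This study will follow-up a group of people with BMI above 30 over a period of one to four years". Section 3.9 gives one main regression, of work on physical activity, diet and life quality, with no term for route. Section 3.10 gives one set of sample sizes for before-after change. For work the target is a "statistically significant change in 25 percent increasing work participation"; the other two are an 11 kg weight loss and a 15D change of 0.02.

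**The concern.** A person who replies to a letter after the programme can do so in the light of the result. Someone who is back at work and lighter may be more willing to sign than someone who is neither. In a single-group study without a comparator, the before-after change has nothing else to be judged against, so selective reply would look like programme effect. The changes exposed to this are those on which section 3.10 sizes the study: work, weight and 15D.

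The main aim is an association, between lifestyle change and work participation. That is threatened too, but under a narrower condition, which the working sets out.

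**Working it through.** **1. What the plan supplies.** The protocol gives neither the share of participants who come by route 2 nor any reply rate, so there is no figure of its own for this bias. Its only relevant figure is the 25 percent work target; the printed interval is centred there, (18.05 + 31.95)/2 = 25.0. The stated 51 participants cannot be re-derived, because no baseline work rate or within-person discordance is given. Nothing below rests on that number.

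**2. Assumptions.** True proportion working at follow-up p = 0.50 in both routes. Route 2 reply rates are r1 (working) and r0 (not working). Route 1 is unselected on outcome. Route 2 makes up a share f of the sample.

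**3. Within route 2.** Observed proportion = p·r1 / [p·r1 + (1 − p)·r0].

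- 60% versus 50%: 0.30 / (0.30 + 0.25) = 0.545, too high by 4.5 points.
- 70% versus 40%: 0.35 / (0.35 + 0.20) = 0.636, too high by 13.6 points.
- Equal rates: 0.50, no bias.

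**4. Both routes together.** Pooled bias = f × route 2 bias.

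| Route 2 share | 60% v 50% | 70% v 40% |
|---|---|---|
| 25% | 1.1 points | 3.4 points |
| 50% | 2.3 points | 6.8 points |
| 75% | 3.4 points | 10.2 points |

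**5. From level to change.** Step 4 concerns the proportion working at follow-up. The bias in the change equals it only if baseline work status is unrelated to who replies, for example if nobody works at baseline. Section 3.2 also admits people merely at risk of sick leave, so some may be working at entry. Suppose 25% work at baseline and all of them still work at follow-up, so that the true change is 25 points. In route 2 the observed baseline is 0.25 × 0.6 / 0.55 = 0.273 or 0.25 × 0.7 / 0.55 = 0.318. The observed change is 0.545 − 0.273 = 0.273 or 0.636 − 0.318 = 0.318, which is 2.3 or 6.8 points too high. With f = 50% this becomes 1.1 or 3.4 points.

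**6. Cross-check with another mechanism.** Suppose reply depends on improvement itself, nobody loses work, and the true gain is π = 0.25. If improvers are r times as likely to reply, the route 2 gain is π·r / (π·r + 1 − π): 0.333 for r = 1.5 and 0.400 for r = 2. For f = 25, 50 and 75% the pooled gain is 27.1, 29.2 and 31.2 points (r = 1.5), or 28.7, 32.5 and 36.3 points (r = 2). That is about 2 to 11 points too high, the same order as step 4.

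**7. The work model.** Among repliers with lifestyle level X, the odds of working equal the true odds times r1(X)/r0(X). If reply depends on work alone, say 60% versus 50% at every X, the factor is 1.2 throughout and cancels from the odds ratio. If it depends on lifestyle alone, the factor is 1. If the reply ratio is 0.7/0.4 = 1.75 among those who changed lifestyle and 0.6/0.5 = 1.2 among those who did not, the route 2 odds ratio is multiplied by 1.75/1.2 = 1.46. Distortion thus needs reply to depend on work and lifestyle jointly.

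**The case against.** The strongest reply is that nothing here is stated wrongly. The design is openly called pseudo-prospective, which makes consent after the fact legitimate, and analysis by route is the kind of detail that a statistical analysis plan may carry. Much of this stands. A reader might infer that route 2 is improper, or that the protocol orders the routes to be pooled. It does neither: pooling is inferred from one group, one model and one set of sample sizes, with silence on route. What the protocol does fix is the two routes and the consent registration. Section 3.3 says that consents are entered in SPSS, but not that route or date is kept, and no later plan can analyse a variable that was not recorded.

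A second reply is that the primary goal is a correlation, not a change. That is correct, and before-after change is not one of the four listed aims. It is, however, what section 3.10 sizes the study on, and section 1.4 promises documentation of results over time.

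Third, not everyone on route 2 knows the outcome. The route includes people still taking part, and section 3.4 uses the word stay both for the four institutional weeks and for the wider programme. Some will consent before T1 or T2. This stands.

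Fourth, nothing in the document shows that successful people reply more often. This also stands.

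Route 2 cannot be set aside as an interview-only route. Its last step mentions a call about the interview, but the letters ask for consent to the study.

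**Conclusion.** The concern holds as a possible bias that the protocol leaves unexamined, not as a demonstrated one. The pooled proportion working at follow-up would be overstated by about 1 to 3, 2 to 7 or 3 to 10 points for a route 2 share of a quarter, a half or three quarters. This rests on 50% truly working and on the assumed reply rates. It falls to zero with equal reply rates and would reverse if people who did badly replied more. When reply depends on follow-up work status, the bias in the change is smaller if some already work at baseline.

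Two stronger readings are tempting. One sets the full 5 to 14 points of step 3 against the 25 percent target. That would require everyone to have come by route 2, would compare a level with a change, and would read 25 percent as percentage points, which section 3.10 does not say. The other holds that the work-model odds ratios are biased; they are only if reply depends jointly on work and lifestyle change.

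Route 2 need not be small: section 1.3 dates the programme to 2015, and the timetable in section 3.14, as far as it can be read, marks questionnaires in 2016 and recruitment in 2017. Its share is not stated. This is a worthwhile improvement of modest weight.

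**What to change.** 1. In section 3.3, have the project secretary record consent date and route (before the stay, during the programme, after the programme) when the consent is registered in SPSS.
2. Report the baseline-to-T2 changes in work, weight and 15D by route. T2 is the last point at which section 3.6 collects these measures.
3. Pre-specify a repeat of the main work model in route 1 participants as a sensitivity analysis, reported whatever it shows. No rule should switch the main claim to one route depending on whether the results differ.

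The cost is two recorded items, one split table and one extra model, with no new participants or visits. The main drawback is precision. If half of the required 51 to 59 participants came by route 1, about 26 to 30 would remain for a three-category outcome with three predictors. Differences between routes may also reflect calendar period, so the comparison is a check and not proof of consent bias.

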3.4 The content of the occupational rehabilitation stay at Muritunet

The participants report data while they are at Muritunet. The rehabilitation stay is as followed with the moment for data collection:

1. Four weeks with an institutional stay at Muritunet (BL)
2. Follow-up:
 - a. Eight weeks, telephone contact between therapist at Muritunet and the participant.
 - b. 16 weeks, video conference on SKYPE between all the participants and a therapist. Lecture on diets.
 - c. 28 weeks, Outpatient stay at Muritunet. Central themes that day is education, conversation, physical test, and forms. (T1)
 - d. 40 weeks, telephone contact between therapist at Muritunet and the participant.
 - e. 52 weeks, Outpatient stay at Muritunet. Central themes that day is education, conversation, physical test, and forms. (T2)

The participants in the occupational rehabilitation program get both practical and theoretical intervention, in groups and individual. Four main themes; cognitive therapy, physical activity, diets and focus on work-oriented approach. The table under shows both groups based activity and personal follow-up.

Group based intervention	In stay	Time	Follow- up	Time
Cognitive approaches in groups	
 - Expectation clarification - Sleep - Cognitive methods - Values, will and choice - Goals setting - Motivation - To come home/ what next/ home - Acceptance and commitment therapy 	11t 2x 1,5 t	Exchange of experience (by 16, 28 and 52 weeks) Acceptance and commitment therapy (by 28 and 52 weeks)	2x 1,5 t 2x 1,5 t
Physical activity in groups	Education- how to exercise Physical activity in a group	1 t 23,5 t		
Diet	Education 
 - Diets - Food knowledge Making food in practice	2t 2,5 t 5 t	Diet, lecture- SKYPE (by 16 weeks)	2 t
Work-oriented approach	Education 
 - Rights and duties at work - Work and health. Individual follow-up	1 t 1,5 t >1 t		
Education, knowledge about obesity	Education 
 - Facts about obesity part one - Facts about obesity part two 	1 t 1 t		
Data-collection	Foams Weight and waist circumference Physical test Skype	1 t 2 t 2 t 1 t	Foams (by 28 and 52 week) Weight and waist circumference (by 28 and 52 weeks) Physical test (by 28 and 52 weeks)	2 t 2 t 2 t
Interdisciplinary intervention (when needed)	Labour consultant, Psychiatric nurse, Physiotherapist, Nutritionist, General Practitioner, Senior Registrar Consultant, Sports Educator, Psychologist, Cognitive Therapist and Occupational Therapist.			
Individual intervention	Phase one	Time	Phase two	Time
Personal approach	Therapeutic contact with: Primary contact person for the stay ACT conversation Labour consultant Nutritionist	4x 0,75 t 6x 0,5t 4x 1t 3x 1t	Prim.contact- conversation (by 4, 28, 40 and 52 weeks)	4 x 0,5t 2 t

	Physiotherapist	4x 1t	Conservation after request with nutrition (by 28 and 52 weeks)	
Contact with work place, NAV or other	Individual after need		Individual after need (by 28 and 52 weeks)	

3.5 Data

This study will use several sources for data to measure changing among the participants. Data from baseline, T1 and T2 will be the foundation to see if there is a correlation between the different factors, as well as to substantiate or to find new findings.

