The primary goal of this trial: What correlation is there between life style changing and work participation after participating in occupational rehabilitation on Muritunet?

Aims of the trial are:

1. Will changes in physical activity, diets, and life quality correlate with work participation?
2. Will changes in physical activity, diets, and return to work self-efficacy correlate with life quality?
3. Will changes in work participation, life quality, and diets correlate with weight changes?
4. What experience the participants as important factors to achieve lifestyle changes and work participation?

Work participation defined in this study is working full time or partial with an employer, permanent or temporary or as a student. The employee has to work coherently in 28 days without to receive social benefits.

Life quality defines in either in a subjective or an objective perspective [29]. In this study, the subjective perspective emphasizes the individual's positive, negative, cognitive and emotional experience that concern life quality.

Diet in this study is the intake of food and liquid that shall ensure a satisfying amount of calories, nutrient and prevent life style diseases.

Physical activity in this study is action made by musculature in a way that it results in increased energy consumption higher than resting.

3 Implementation

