2. T1, six months after the first stay at Muritunet. Data gathered from the journal, from self-reported forms, and from a physical test. The particular data package is; in and out date for the stay, diagnosis, health problems, work status, social benefits, changing in work status, work place, expected work time pr. Week and occupation code, work motivation, income, diet, physical capacity and activity, life quality and overeating behaviour.
3. T2, 12 months after the first stay at Muritunet. Data gathered from the journal, from self-reported forms, and from a physical test. The particular data package is; in and out date for the stay, diagnosis, health problems, work status, social benefits, changing in work status, work place, expected work time pr. Week and occupation code, work motivation, income, diet, physical capacity and activity, life quality and overeating behaviour.
4. T3, Focus group interview, one to four years after the participants finishing their stay at Muritunet.

5. T4, Data collecting from Norwegian patient register (NPR) and National Education database (NUDB). Will be collected once. Data collected are social benefits as sick leave, work assessment allowance, disability benefits, unemployment benefits, diagnosis for sick leave, changing in work employment, work place and expected work time pr. A week and occupation code.

Some participants will return to their work, but some will not. It will lead to variation for my chose of how to design methods and analyze the data material. Different ways will complete each other, and today it is common to use several methods and models in the same study.

Data analysis is chosen on the background of design and approaches. BL, T1, and T2 is a typical quantitative approach and will be analyzed both on its own, but also compared with data collected in T3 and T4. The qualitative interview will have open-ended questions, and the participants will get the opportunity to reflect on themes defined from the data collection earlier in the study.

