3.6 Quantitative data collection

Foams register and explain changing in life style factors and work participation. The physical test may say something about the participant's physical capacity. In this study foams and a test will measure conditions that affect socio- economic, demographic and individual factors, their expectation of returning to work, the motivation for working and sick-leave, physical activity, physical and mental health, diet and nutrition, and life quality. Information about the date of the stay, diagnoses, and activity is in the journal at Muritunet.

Areas	Time of data collection	Foams
Employment data	BL	ARR foam, socio-demographic data and work status (Nasjonal kompetansestest for arbeidsretta rehabilitering)
	BL, T1 and T2	Short ARR foam
	BL	Return to work self- efficacy (RTWSE 19) [31]
Health data	BL	High, waist circumference, body fat percentage and fat-free mass kg
	BL, T1, and T2	Weight, BMI
	BL	Diagnoses
	BL	Subjective Health Complaints (SCH 25) [32].
Physical capacity	BL	Step-test with Borg scale CR 10
	BL, T1, and T2	Registration of level of physical activity(Health Directorate)
Quality of life	BL, T1, and T2	Quality of life (15D) [33].
Food habits	BL	Thoughts and feelings about food, body and eating behavior. Survey about Binge eating disorder (EDO)[34].
	BL, T1, and T2	Food behavior registration (Health Directorate)

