3.9 Analyse

The goal of this study is to explore the correlation between life style changing and work participation. Four secondary issues will result in using different ways of analyzing the data material. In this way, each issue can be investigated on their own, but also analyzed with each other.

The primary analyzing approach for this study is multivariate logistics regression analysis with a focus on the correlation between several independent variables (X) and dependent variables (Y). In the main issue Y= work, and X= physical activity (x1), diets (x2) and life quality (x3). Work divides into three categories; a) full time working, b) part time working, c) not working. In the secondary issue, is Y= life quality and X= physical activity (x1), diets (x2), and the belief in managing (x3).

In the quality research, thematic methods will be used to analyze the interviews. This method can catch the significant complexity in the text and is the most usual way to analyze a text in qualitative research. This way of analyzing consist of six steps. 1. Transcribing data, 2. Reading and re-reading the data, 3. Coding, 4. Search after subjects, 5. Define and give a name to the subjects, and 6. Choose to illustrate examples of different issues.

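### Section 3.9 does not say how three visits per person enter the logistic model or which visits define outcome and predictors; a repeated-measures model of change would use both follow-ups validly

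*Protocol*

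**What the plan says.** Section 3.5 of the protocol: "Data from baseline, T1 and T2 will be the foundation to see if there is a correlation between the different factors". The table in section 3.6 lists the short ARR form (work status), physical activity, food behaviour and 15D at BL, T1 and T2, so every variable of the main model exists three times per person.

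Section 3.9: "The primary analyzing approach for this study is multivariate logistics regression analysis". For the main question the outcome is work, and the predictors are physical activity, diet and life quality. "Work divides into three categories; a) full time working, b) part time working, c) not working". For the secondary question, life quality takes the place of Y under the same approach. No visit, time or person term is listed, and no visit is attached to Y or to the predictors.

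The first aim in section 2 is about change: "Will changes in physical activity, diets, and life quality correlate with work participation"? Section 3.10 bases the sample size on two time points and asks for 51 (work), 59 (weight) and 55 (quality of life) participants.

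Other analyses are announced but not named. Section 3.9: "Four secondary issues will result in using different ways of analyzing the data material". Section 3.1: "today it is common to use several methods and models in the same study".

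**The concern.** The protocol names its primary model and writes out the variables, but that model does not match the data structure of sections 3.5 and 3.6. Three sections point in different directions. Section 2 asks about changes, section 3.5 uses three visits, and section 3.9 writes outcome and predictors as levels with no visit attached. An analyst who follows section 3.9 literally could stack three records per person, or could pick one pair of visits.

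The choice matters. Records from the same person are usually alike. Counting them as independent usually makes standard errors too small and can produce false associations between lifestyle and work. Using one follow-up visit is valid but gives up information in a cohort of only 51 to 59 people.

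A related mismatch is that 15D is a score (section 3.10 works with changes of 0.02 and 0.015). It does not fit a logistic model unless it is cut into categories.

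**Working it through.** **Inputs.** From the protocol: three visits (3.5, 3.6), three work categories and three predictors (3.9), 51 to 59 people (3.10), significance level 0.05 (3.10; two-sided assumed). The protocol gives no within-person correlation, so all correlations below are assumptions. It also gives no figure for this point that could be reproduced. The power figures in 3.10 rest on one change per person and are not used here.

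**1. Stacking, by formula.** With m records per person and within-person correlations ρx (predictor) and ρy (outcome), the variance is understated by

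DE = 1 + (m − 1)·ρx·ρy,

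and the true level of a nominal 5% test is 2[1 − Φ(1.96/√DE)]. If work is a latent normal variable cut at its median with latent correlation ρ, then ρy = (2/π)·arcsin(ρ). With m = 3 and ρx = ρ:

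- ρ = 0.5: ρy = 0.333, DE = 1 + 2·0.5·0.333 = 1.333, √DE = 1.155, level 9.0%.
- ρ = 0.8: ρy = 0.590, DE = 1 + 2·0.8·0.590 = 1.944, √DE = 1.394, level 16.0%.

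If a predictor never changes within a person (ρx = 1), DE = 1 + 2ρy. For ρy = 0.3, 0.5 and 0.8 this is 1.6, 2.0 and 2.6, and the level is 12%, 17% and 22%. If ρx = 0, DE = 1 and there is no inflation.

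**2. Stacking, by simulation.** No true association, binary work status, one predictor, 1,500 data sets per row. The last column is one row per person: work at T2 on the change in the predictor from baseline to T2.

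| People | Outcome corr. (latent) | Predictor corr. | Stacked, naive | Stacked, clustered | Change, one row |
|---|---|---|---|---|---|
| 51 | 0.5 | 0 | 4.3% | 4.9% | 3.5% |
| 51 | 0.5 | 0.5 | 8.1% | 5.4% | 4.0% |
| 51 | 0.8 | 0.5 | 12.6% | 5.8% | 4.5% |
| 51 | 0.8 | 0.8 | 15.3% | 5.7% | 4.3% |
| 59 | 0.5 | 0 | 4.5% | 4.9% | 3.8% |
| 59 | 0.5 | 0.5 | 8.3% | 4.7% | 5.1% |
| 59 | 0.8 | 0.5 | 11.4% | 5.3% | 4.9% |
| 59 | 0.8 | 0.8 | 15.9% | 5.9% | 4.7% |

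The simulation error near 5% is √(0.05·0.95/1500) = 0.6 percentage points. A separate simulation with 55 people and 4,000 data sets per setting gave 8.6% at 0.5 and 15.7% at 0.8 for the naive test, and 4.8% at both with clustering. Formula and both simulations agree.

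**3. One follow-up visit or two.** The ratio of the standard error with two visits to that with one is √[(1 + ρx·ρy)/2].

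- ρ = 0.5: √[(1 + 0.167)/2] = 0.76, so 24% smaller.
- ρ = 0.9: ρy = 0.713, √[(1 + 0.642)/2] = 0.91, so 9% smaller.

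The 55-person simulation gave ratios of 0.73 at 0.5 and 0.89 at 0.9, so 27% and 11% smaller. Together, about 10 to 27%. These figures come from a model of levels with one predictor and carry over to a model of change only approximately.

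**4. Size of the proposed model.** One visit term, two terms for baseline work status (three categories) and six for the baseline value and change of three predictors make 1 + 2 + 6 = 9 slopes, if each predictor is a single score. An ordinal model adds two thresholds, 11 parameters in all. A multinomial model needs 2·9 + 2 = 20. With 51 to 59 people there are 102 to 118 follow-up rows.

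**The case against.** A reader might infer that the protocol fits an ordinary logistic model which treats each visit as a different person, so that it must either overstate precision or throw a visit away. The text does not support that.

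- Section 3.9 does not say ordinary, does not define a record, and nowhere says that visits are stacked.
- The aims speak of changes and the sample size uses two time points. Both fit one row per person, and that model holds its level (3.5 to 5.1% in the table).
- The alternatives are not exhaustive. Changes to T1 and to T2 can both be predictors in one row, or each follow-up can have its own model. Work data may also come from the registers (T4, section 3.7).
- Other methods are announced, and clustering or random effects are often left to a statistical analysis plan, which is not shown here. Their absence alone is not a defect.
- The error rates depend on stacking and on assumed correlations. They were simulated with a binary outcome and one predictor, not three categories and three predictors.

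All of this stands, and it rules out a claim that the planned analysis is invalid. It does not settle which visits define Y and the predictors. Section 3.10 does not settle it either, because it labels the end of the intervention T3, which section 3.1 uses for the focus group interview. The one-row alternatives have costs of their own. Entering both changes doubles the change slopes from 3 to 6 (from 6 to 12 in a multinomial model) and still uses work status at one visit. Separate models double the tests and give no single answer to the primary question.

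**Conclusion.** The point holds as a worthwhile and inexpensive improvement, not as a demonstrated error. Sections 2, 3.5 and 3.9 do not fix which visits define outcome and predictors, or how three visits per person enter the named model.

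If the visits were stacked as independent records, a nominal 5% test would run at roughly 8 to 16% for assumed equal within-person correlations of 0.5 to 0.8. It would run higher for predictors that hardly change within a person, and at about 4% for predictors uncorrelated within person. A model of change from baseline to T2 with one row per person is valid but leaves T1 unused. Using two follow-up visits instead of one makes the standard error about 10 to 27% smaller at assumed correlations of 0.9 down to 0.5, provided the association is the same at T1 and T2. A clustered analysis of both follow-ups avoids the first problem and recovers the second.

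**What to change.** In section 3.9:

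1. State that the outcome is work status at T1 and T2, with one row per person per follow-up visit.
2. Name an ordinal logistic model (multinomial if the ordering of the categories is not tenable), fitted by GEE or with a random person effect, with standard errors clustered on person.
3. Include a visit term, baseline work status, and both the baseline value and the change from baseline of activity, diet and 15D. The change terms are needed so that the model answers the aim; levels alone would mix differences between people with changes within them.
4. When 15D is the outcome, use a linear mixed model with a visit term and a person effect instead of logistic regression. The table in 3.6 records return-to-work self-efficacy at BL only, so it can enter that model only as a baseline value.
5. Align the visit labels in sections 3.1, 3.9 and 3.10.

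The cost is wording and a standard procedure in common software; no new data are needed. Reporting becomes slightly more complex, and the model assumes a common association at T1 and T2. With 51 to 59 people the number of terms must stay small, which favours the ordinal form, or a small-sample correction to the clustered standard errors should be used. The return to about 5% was shown only for a simpler model.
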